5.6.1.1.5 Study Flow 50htn 50dm 30-40 BMI

5.7 Participant Retention

All patients will be encouraged to complete study follow-up, and all reasonable efforts will be made to ensure completeness of follow-up.

It is understood that study participants may withdraw consent for study participation at any time irrespective of their reasons. The investigators may also withdraw a participant from the study in order to protect their safety or adverse device effects, and/or if they are unwilling or unable to comply with the required study procedures.

In the event of a patient withdrawing from the trial, the reason for withdrawal must be documented on the CRF.

5.8 Replacement of withdrawn subjects

Patients withdrawn prior to ESG or LS will not count towards the target enrollment. New patients will be randomized to target enrollment of 200 total patients receiving ESG or LS. The power and sample size calculation includes additional patients to improve power assuming some post-intervention dropout.

5.9 Source Documentation

Study case report forms will be used as source documentation for the trial for all participant follow-up visits. Source documentation from the electronic medical record will be required for the ESG procedure(s), medications, and any serious adverse medical events. Any additional pertinent documentation regarding the patient's trial participation will be also be required to be filed in the subject binder.

6 DATA MONITORING AND SAFETY REPORTING

6.1 Data Monitoring Committee

An independent Data Monitoring Committee (DMC) will serve as an autonomous advisory group for the trial. The DMC will be responsible for safeguarding the interests of trial participants, assessing the safety and efficacy of the interventions during the trial, adjudication of Adverse Events, and for monitoring the overall conduct of the clinical trial. The DMC may also provide recommendations about stopping or continuing the trial. To contribute to enhancing the integrity of the trial, the DMC may also formulate recommendations relating to the selection/recruitment/retention of participants, their management, improving adherence to protocol-specified regimens and retention of participants, and the procedures for data management and quality control.

The DMC members appointed for this trial consist of individuals who collectively have experience and expertise in the management of patients with obesity, experience in randomized clinical trials with endoscopic devices, experience in safety monitoring and absence of significant conflicts of interest or participation in the trial.

The first DMC meeting will occur once 25 participants have undergone the ESG. Subsequent DMC meetings will be scheduled every four months while the trial is actively going.

The DMC will be led by [name], a world leader in bariatric and metabolic surgery at Florida International University and past president of the International Federation of Bariatric Surgery.

6.1.1 Stopping rules

The study will be stopped if a) one death attributed to the procedure or the device, b) >1% of Grade IV AEs has occurred, and c) if > 5% Grade III or more AEs occur.

6.2 Adverse Events

6.2.1 Definitions

The following definitions will be used:

6.2.1.2 Adverse Event:

Any untoward medical occurrence, unintended disease or injury, or untoward clinical signs (including abnormal laboratory findings) whether or not related to the study intervention. Each subject will be followed closely to ensure safety.

Adverse events will be classified using the Clavien-Dindo classification.

Grade	Definition
Grade I	Any deviation from the normal postoperative course without the need for pharmacological treatment or surgical, endoscopic, and radiological interventions Allowed therapeutic regimens are: drugs as antiemetics, antipyretics, analgetics, diuretics, electrolytes, and physiotherapy. This grade also includes wound infections opened at the bedside
Grade II	Requiring pharmacological treatment with drugs other than such allowed for grade I complications Blood transfusions and total parenteral nutrition are also included
Grade III	Requiring surgical, endoscopic, or radiological intervention
Grade IIIa	Intervention not under general anesthesia
Grade IIIb	Intervention under general anesthesia
Grade IV	Life-threatening complication (including CNS complications) requiring IC/ICU management
Grade IVa	Single organ dysfunction (including dialysis)
Grade IVb	Multiorgan dysfunction
Grade V	Death of a patient

6.2.1.2.1 Treatment Criteria

6.2.1.2.1.1 Thiamine Replacement

Criteria for thiamine replacement for suspected or established vitamin B₁ deficiency on subjects with uncontrolled nausea and/or vomiting:

- Vomiting post ESG continues 7 days or more after EGS, in ability to take down adequate levels of hydration. Defined as vomiting >2 x a day.
- Nausea post ESG continues 7 days, daily with the inability to drink due to nausea, unrelieved by nausea medication, and continuing 7 days or more.

Thiamine replacement²⁶:

- Hospitalization: 500 mg per day thiamine IV push for 3-5 day followed by 250 mg per day IV push + multivitamin in 1 L NS q day while in the hospital.
- Outpatient: Thiamine 100 mg TID daily for 3 months.

6.2.1.3 Serious Adverse Event (SAE):

An adverse event that meets one of the following criteria

- Led to death
- Resulted in serious deterioration in the health of the subject that results in:
 - Life-threatening illness or injury
 - Permanent impairment of a body structure or a body function

- The need for in-patient care or prolongation of hospitalization (this does not include the optional 23 hours observation admission after ESG or re-tightening procedure).
- Medical or surgical intervention to prevent life-threatening illness or injury or permanent impairment to a body structure or a body function.
- **Planned hospitalization for a pre-existing condition, or a procedure required by the trial protocol, without serious deterioration in health, is not considered a serious adverse event**

Unanticipated problems, SAEs and AEs will be reported to governing IRBs per local guidelines.

6.2.1.4 Device-Related Adverse Event (DRAE):

An adverse event related to the use of the medical device. This definition includes any events resulting from incorrect delivery and operation of the device and/or of its approved accessories, or any malfunction of the device or its components. This definition also includes any event resulting from user error or from intentional misuse of the device.

6.2.1.5 Serious Device-Related Adverse Event (SDRAE):

Any untoward medical occurrence that can be attributed wholly or partly to the device, which resulted in any of the characteristics of a serious adverse event as described above.

6.2.1.6 Unanticipated Adverse Device Effects (UADE):

Any adverse device effect which by its nature, incidence, severity or outcome, has not been identified under the SAE section 6.2.

6.3 Protocol Deviations

All protocol deviations will be documented with the subject number and date of the protocol deviation. The following information will be documented for each protocol deviation:

- Inclusion/Exclusion exceptions or violations, including subject did not sign informed consent prior to study admission
- Follow-up visit not performed or Follow-up outside of window
- Required testing or questionnaire not performed
- Other (Describe)

Protocol deviations should be reported to the lead institutions within 72 hours of noting the deviation.

7 STATISTICAL ANALYSIS

7.1 Power and Sample Size

The primary endpoint for power and sample size is %EWL at 12 months. The null hypothesis is no difference in mean %EWL between ESG and LS randomized arms ($H_0: \mu_t = \mu_c$ where μ_t is the average %EWL in the ESG group and μ_c is average %EWL in the LS group). We will perform a two-sided hypothesis test at alpha level 0.05 (alternative hypothesis $H_a: \mu_t \neq \mu_c$) Based on the published literature with the ESG technique a conservative presumption is 25% EWL in the ESG arm with a standard deviation (SD) of 30% at 12 months compared to 10% EWL on LS alone with SD of 5%. We plan a 1:1.5 randomization scheme that allocates 3 patients to LS for every 2 to ESG at the time of randomization. Based on a two-sample t-test with unequal variances and two-sided alpha=0.05, we would have 80% power to detect a difference of 15% in average %EWL between groups with 34 patients allocated to ESG and 51 randomized to LS. 90% power would require group sizes of 45 and 68, respectively. To allow for dropout, and more importantly, to power exploratory aims for obesity comorbidity subgroups, we propose the initial randomization of 200 patients – 80 to ESG and 120 to LS.

120 subjects are initially randomized to LS in level 1. Of these, we anticipate up to 20% will achieve a successful decrease of $\geq 25\%$ in %EWL through LS alone at 12 months. Further, we anticipate up to 20% may be lost to follow up or drop out prior to 12 month follow up. Thus, we anticipate at least 77 ($120 * 0.8 * 0.8$) subjects to continue to level 2 and be offered ESG. We will test the one-sample hypothesis (non-randomized) that of those offered ESG at 12 months, average change in %EWL will be at least 10%. Based on a one-sample t-test with two-sided alpha=0.05 and standard deviation at 24 months of 30%, 70 subjects completing ESG would have 98% power to detect an effect of 25% reduction in %EWL.

7.2 Statistical Analysis

Statistical analyses of randomized groups at 12 months will be performed based on a modified intent-to-treat (mITT) principle for efficacy analyses. Patients randomized but subsequently withdrawn or identified as meeting exclusion criteria prior to intervention (as applied to both the treatment and control arms) will be excluded from the analysis if the reason for exclusion is documented and unrelated to the randomized arm.

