5.4 Randomization

Participants will be stratified to three groups (Obesity, Obesity HTN, and Obesity DM) and will be randomly assigned to treatment or control group with a 1:1.5 allocation per a computer generated randomization using variable block randomization.

Participants will be notified of their randomization assignment on the day of the randomization visit. Participants randomized to the control group will proceed to an appointment with the dietitian for their Week 1 visit on the day of randomization. Participants randomized to the treatment group will proceed to a brief visit with the dietitian to review the post-op liquid diet, and the ESG will be scheduled within 30 days of randomization. Participants of child-bearing potential will be required to have a pregnancy test within 7 days of the scheduled ESG.

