7.2.3 Secondary Analyses

A per-protocol analysis will compare ESG to LS randomized groups among protocol adherent patients – here, defined among ESG randomized patients as those actually receiving the procedure and making $\geq 80\%$ follow-up visit in both treatment and control groups. Modified ITT will be considered the primary approach for all efficacy analyses, and will include patients who actually receive the ESG or started the life-style program regardless of adherence to follow-up visits. Safety endpoints and adverse events may be evaluated based on treated group (per-protocol).

Additional analyses may assess the moderating effect of HTN and DM on the effect of ESG vs LS at 12 months. Linear regression will include an interaction between HTN (or DM) and randomized group to determine the effect of ESG in subgroups and whether the effect is different between HTN and non-HTN (also, separately, DM and non-DM) patients.

Additional outcomes and analyses not specified here are considered exploratory and post-hoc and will be clearly identified as such in any publications.

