7.3 Missing Data

The primary analysis uses a hierarchical regression model, assuming post-randomization dropout is missing at random (MAR) among subjects completing at least 1 of the 11 planned follow up visits.

Patients excluded after randomization and before ESG/LS on the basis of identified exclusion criteria will be excluded from analyses; reasons for meeting exclusion criteria will be documented. Patients that withdraw/dropout between randomization and ESG/LS are assumed to be missing completely at random. However, a sensitivity analysis will compare withdrawn subjects to participating subjects and perform analyses under MAR (including multiple imputation) assumptions if these subjects appear different or if dropout occurs at substantially different rate in one arm compared to the other. Participating patients who dropout prior to the first follow up visit will be analyzed similarly.

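### The plan does not settle whether an ESG assignee who never receives ESG for an arm-related reason is in the primary analysis, and no unconditional all-randomized analysis stands beside the mITT result

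*Combined protocol and SAP*

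**What the plan says.** Three places in the combined protocol and SAP govern patients lost between randomization and the start of the intervention.

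- **Section 7.2** addresses "Patients randomized but subsequently withdrawn or identified as meeting exclusion criteria prior to intervention (as applied to both the treatment and control arms". Such patients "will be excluded from the analysis if the reason for exclusion is documented and unrelated to the randomized arm". By implication, a loss whose reason is related to the arm stays in.
- **Section 7.2.3** says that the mITT set "will include patients who actually receive the ESG or started the life-style program regardless of adherence to follow-up visits". The reason for not starting plays no part.
- **Section 7.3** splits by cause. For late-found ineligibility: "Patients excluded after randomization and before ESG/LS on the basis of identified exclusion criteria will be excluded from analyses". The reason must be documented, but nothing is said about relation to the arm. For the rest: "Patients that withdraw/dropout between randomization and ESG/LS are assumed to be missing completely at random".

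Section 7.3 then adds a safeguard: "However, a sensitivity analysis will compare withdrawn subjects to participating subjects". Analyses under missing at random (MAR), including multiple imputation, follow "if these subjects appear different or if dropout occurs at substantially different rate in one arm compared to the other".

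On timing, Section 5.4 states: "Participants will be notified of their randomization assignment on the day of the randomization visit". Controls have their Week 1 dietitian visit that same day. ESG is scheduled within 30 days and, under Section 5.5 (Treatment Group), follows an upper endoscopy looking for contraindications. Endoscopy is not listed at screening (Section 5.3), and the Level 1 control schedule has no entry for it. Section 5.8 replaces patients withdrawn before ESG or LS, so the target of 200 counts patients who receive an intervention.

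**The concern.** The trial is open-label and the two arms are exposed differently before treatment starts. A control has almost no interval in which to drop out before LS. An ESG assignee knows the assignment, may wait up to a month, and then has an examination that can bar the procedure. Several exclusion criteria in Section 4.6, such as larger gastric polyps, a large hiatal hernia or severe esophagitis, are findings that this endoscopy can reveal. After randomization they are routinely looked for in the ESG arm only.

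If those who never start are removed, the primary comparison is between starters. If they are kept, it is close to the effect of assignment. The two can differ, and the plan should say in advance which one it reports. As written, it can be followed in either way, and no by-assignment result is guaranteed beside the mITT estimate.

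**Working it through.** **Step 1. Apply the rules to two ESG assignees who never receive ESG.**

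| Patient | 7.2 | 7.2.3 (natural reading) | 7.3 |
|---|---|---|---|
| Declines because of the assignment | In: reason related to arm | Out: ESG not received | Assumed missing completely at random; possible imputation |
| Contraindication found at the pre-ESG endoscopy | Depends on whether a finding made at an ESG-only examination counts as related to arm | Out | Out, with no arm condition |

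For membership of the primary set there are two outcomes, in or out. The firm conflict is the first row.

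**Step 2. Reproduce the plan's power (Section 7.1).** Inputs: ESG mean 25, SD 30; LS mean 10, SD 5; two-sided alpha 0.05; t-test with unequal variances. Using the noncentral t with Satterthwaite degrees of freedom, and SE = sqrt(30²/n_ESG + 5²/n_LS):

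- 34/51: SE 5.19, power 80.1% (plan: 80%).
- 45/68: SE 4.51, power 90.2% (plan: 90%).
- 80/120, nobody removed: SE 3.39, power 99.2%.

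**Step 3. Difference by assignment if some ESG assignees never start.** Let x be the share removed from the ESG arm only and u their mean %EWL. The documents give neither; x = 5%, 10%, 20% and u = 10 (LS-like) or 0 (no loss) are assumptions. Those removed are given an assumed SD of 5.

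- Difference = (1 − x)·25 + x·u − 10
- ESG-arm variance = (1 − x)·900 + x·25 + x(1 − x)(25 − u)²

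| x | u | Difference by assignment | Difference under mITT | ESG-arm SD | Power against zero, 80/120 |
|---|---|---|---|---|---|
| 5% | 10 | 14.25 | 15 | 29.4 | 98.9% |
| 10% | 10 | 13.5 | 15 | 28.9 | 98.4% |
| 20% | 10 | 12.0 | 15 | 27.6 | 96.7% |
| 5% | 0 | 13.75 | 15 | 29.8 | 98.1% |
| 10% | 0 | 12.5 | 15 | 29.5 | 96.0% |
| 20% | 0 | 10.0 | 15 | 28.7 | 86.1% |

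Example for 20% and no loss: 0.8 × 25 + 0.2 × 0 − 10 = 10.0.

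**Step 4. The same check at the clinical results the protocol cites.** Section 2.2 reports 18% TBWL at 12 months. With an ideal BMI of 25 (Section 2.3), %EWL = 0.18 × BMI/(BMI − 25) × 100. That is 0.18 × 40/15 = 48% at BMI 40 and 0.18 × 35/10 = 63% at BMI 35. Even with 20% removed and losing nothing, the lower figure leaves 0.8 × 48 − 10 = 28.4 points.

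**Step 5. What the safeguard in 7.3 covers.** The comparison of withdrawn with participating subjects is a commitment. The MAR and imputation step runs only on a trigger that has no numeric threshold. It is worded for withdrawals and does not clearly reach eligibility exclusions. The other analysis set in 7.2.3 is per-protocol, which is narrower than mITT.

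**The case against.** The strongest reply is that Section 7.2 is the governing statement. It applies to both arms and demands a documented reason unrelated to arm, so later sections need not repeat the condition. Section 7.2.3 says that mITT includes starters, not that it includes only starters. It follows a per-protocol definition based on visit attendance, so it may be drawing only that contrast. Reasons for withdrawal are already collected (Sections 5.7 and 7.3), and 7.3 plans a comparison and a conditional imputation.

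Much of this stands, and it limits the point. It does not settle which reading applies, nor does it make the wider analysis certain to appear.

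Four stronger readings are tempting, and the documents do not support them.

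- **That the three sections give three different answers for the same patient.** They are three rules with two outcomes, and 7.3 largely agrees with the natural reading of 7.2.3.
- **That no sensitivity analysis is planned.** One is; the gap is that its imputation step is conditional.
- **That the mITT estimate is shown to be biased upward.** No removal rate or outcome is given for either arm. For assignees found ineligible at endoscopy, the gap is mainly a different target population and is not shown to be bias.
- **That the 15-point societal benchmark would be wrongly passed.** Section 2.3 words it as procedure against control and does not specify a comparison by assignment. Section 7 plans no test against 15; the primary test is against zero (Sections 4.2.1 and 7.1). The planning means happen to sit exactly 15 points apart, which is why any removal in Step 3 falls below that value. Section 7.1 calls its ESG assumption conservative.

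**Conclusion.** The point holds as a cheap improvement. Membership of the primary set is unresolved for ESG assignees who do not start for an arm-related reason, the opportunity for such loss is unequal by design, and no by-assignment result is guaranteed. The concern is mainly arm-related withdrawal.

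In the assumed range the estimate could differ by 0.75 to 5 points (15 − 14.25 to 15 − 10.0). Those sizes rest on assumed removal shares, assumed outcomes for those removed, removal from the ESG arm only, and the planning means. The conclusion of the test against zero is little affected, and at the results cited in Section 2.2 the difference stays well above 15. Power is no obstacle to the extra analysis.

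**What to change.** 1. Reconcile Sections 7.2, 7.2.3 and 7.3 into one mITT definition. State whether assignees found ineligible at the pre-ESG endoscopy are in or out. Keep the rule in 7.2 that losses for arm-related reasons, such as declining the assigned procedure, stay in.
2. Keep mITT primary and add one mandatory, unconditional supporting analysis of all randomized participants by assigned arm, including those replaced under Section 5.8. Use week-52 weights from non-starters where they can be obtained. Otherwise impute conditionally on treatment received or with LS as the reference, and show no weight loss as a bound. Imputation by assigned arm alone would give non-starters the outcomes of treated patients. Report the result beside mITT, including wherever the 15-point difference is discussed, without making it the deciding estimate.
3. Report pre-intervention losses by arm and reason, with endoscopic ineligibility separate from withdrawal.

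The cost is some SAP wording, a little more analysis work, a few extra week-52 weights, and possibly a slightly smaller supporting estimate.

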7.2.1 Primary Aim

The primary outcome is %EWL at 12 months assessed in the two randomized arms. A hierarchical linear regression model will be fitted to post-randomization %EWL measurements, planned for 11 post-randomization timepoints through 12 months. Post-randomization outcomes will be modeled as a function of discrete visit (instead of assuming a linear or other functional form of time since randomization) and treatment indicator variables. Models will also adjust for age, sex, baseline BMI, HTN, and DM status to reduce residual variation and improve power. The primary outcome comparison at 12 months is estimated from a linear combination of treatment and time indicators. A spatial autocorrelation covariance structure will be used.

Assumptions for normality of residuals and homoscedastic variance will be assessed; hierarchical median regression (Geraci and Bottai, 2014) will be considered under significant violations.

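### Section 7.1 plans for very unequal SDs in the two arms, but the primary model in 7.2.1 assumes equal variance and sets out no response that keeps the comparison of means

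*Combined protocol and SAP*

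**What the plan says.** Section 7.1 presumes a mean of 25% EWL on ESG "with a standard deviation (SD) of 30% at 12 months compared to 10% EWL on LS alone with SD of 5"%. The group sizes are "Based on a two-sample t-test with unequal variances and two-sided alpha=0.05". Allocation is 2:3, with 80 patients to ESG and 120 to LS.

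Section 7.2.1 fits a hierarchical linear model to the repeated %EWL measurements. On covariance it says only "A spatial autocorrelation covariance structure will be used". The week-52 result is defined as follows: "The primary outcome comparison at 12 months is estimated from a linear combination of treatment and time indicators". On assumptions it says "Assumptions for normality of residuals and homoscedastic variance will be assessed; hierarchical median regression" (a method reference follows) "will be considered under significant violations". Sections 7.2, 7.2.2, 7.2.3 and 7.3 add no arm-specific variance and no robust standard error for this analysis.

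The null hypothesis in 4.2.1 and 7.1 concerns mean %EWL. So does the society criterion in 2.3, which asks for a difference in means of at least 15 points that is also statistically significant.

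**The concern.** The planning SDs differ sixfold, which is a 36-fold ratio of variances. The sponsor therefore expects the equal-variance assumption of its own primary model to fail, yet the plan does not settle what happens then. It gives no test or threshold for a violation, and the one named remedy is only to be considered. The choice is left until the data are seen, in an open-label trial with a single primary test.

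Two of the possible responses are unsatisfactory:

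- **Keeping one common variance.** The arm with the larger planned SD is the smaller arm. That is the direction in which a pooled variance understates the standard error. A random effect with the same variance in both arms would not remove this.
- **Replacing the model with median regression.** The contrast would then concern medians, while the null and the society threshold concern means. Unequal variance alone is no reason to give up the mean.

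At stake are the coverage of the primary confidence interval, the nominal 5% error rate and the quantity being estimated.

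**Working it through.** **Inputs.** From 7.1: SDs 30 (ESG) and 5 (LS), means 25 and 10, two-sided alpha 0.05, planned sizes 80 and 120. Also from 7.1, for LS: "we anticipate up to 20% will achieve a successful decrease of" at least 25% EWL on lifestyle alone, and "we anticipate up to 20% may be lost to follow up or drop out prior to 12 month follow up".

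**Step 1: the plan's own figures.** The unequal-variance t-test uses SE = √(s₁²/n₁ + s₂²/n₂) with Satterthwaite degrees of freedom and a noncentral t. At 34/51, SE = √(900/34 + 25/51) = 5.19 and power for 15 points is 80.1%. At 45/68 it is 90.2%. The stated sizes reproduce.

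**Step 2: a common variance at 80:120, SDs 30 and 5.** Take complete data, a separate mean for each arm at each visit, SDs constant over visits, and the planning SDs as week-52 residual SDs. The week-52 contrast is then the difference of the two arm means, whatever within-patient correlation the arms share.

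- Pooled variance = (79×900 + 119×25)/198 = 374.1, so the pooled SD is 19.34.
- Model SE = 19.34 × √(1/80 + 1/120) = 2.79.
- True SE = √(900/80 + 25/120) = 3.39.
- Ratio = 0.825. The 95% half-width is 1.96 × 2.79 = 5.5 points, where 1.96 × 3.39 = 6.6 is needed.
- Type I error = 2(1 − Φ(1.96 × 0.825)) = 10.6%, so coverage is about 89%.

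Simulation agrees. A pooled t-test gave 10.6%, and an 11-visit model with common variance and autoregressive correlation 0.9 gave 10.3%. Arm-specific variances gave about 5% in both.

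**Step 3: how far this depends on the LS SD.** Section 7.1 itself casts doubt on an LS SD of 5. Under normality with mean 10, the share reaching 25% EWL is 1 − Φ(15/5) = 0.13%, or 0.2 of 120 patients. The section allows for up to 20%, or 24 of 120. A full 20% implies an SD of 15/0.842 = 17.8. With ESG SD 30 at 80:120:

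| LS SD | Model SE | True SE | Type I error |
|---|---|---|---|
| 5 | 2.79 | 3.39 | 10.6% |
| 10 | 2.96 | 3.48 | 9.6% |
| 17.8 | 3.38 | 3.73 | 7.5% |
| 20 | 3.53 | 3.82 | 7.0% |
| 25 | 3.91 | 4.06 | 5.9% |
| 30 | 4.33 | 4.33 | 5.0% |

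The ESG SD matters too. With LS SD 17.8, an ESG SD of 25 (assumed) gives 6.6% and one of 20 (assumed) gives 5.5%.

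**Step 4: effect on the decision.** At the planned difference, 15/3.39 = 4.4 true standard errors.

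**Step 5: power with unequal variances.** For 15 points, power is 99.2% at 80:120. It is 97.4% at 64:96, which applies the 20% loss to both arms although 7.1 states it for LS only. With LS SD 17.8 the figures are 97.9% and 94.5%.

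**Step 6: are robust standard errors enough?** One arm was simulated with SD rising to 30 by week 52, about 20% dropout depending on the last observed value, and correlation 0.90 to 0.98 per 4 weeks (all assumed). A constant-variance fit biased the week-52 mean by roughly 1 to 2 points. Correct by-visit variances left 0.2 or less. Robust standard errors correct the width of the interval but not that bias.

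**The case against.** The strongest reply is that the plan never says a common variance will be fitted. It says the assumption will be assessed, and a later analyst could choose arm-specific variances. This stands, and it makes every inflation figure conditional. A reader might infer that the primary test has a 10.6% error rate as planned. The documents do not support that: it requires both a common-variance fit and a true LS SD of 5. What remains is that equal variance is the stated assumption, no alternative is given, and following the text as written leads to an interval that is too narrow.

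Second, the SDs are planning figures. The value 17.8 also rests on normality, on a mean of 10, and on reading an upper bound as an expectation. This stands as well, which is why the table runs to equal SDs, where the problem vanishes.

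Third, the SDs were stated alongside different means. If ESG had no effect of any kind, the spreads would be equal and the test nominal. The inflation therefore belongs to the null of equal means with unequal spread. The coverage problem is unaffected by this.

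Fourth, ESG would probably win anyway, and the criterion in 2.3 asks for a difference of 15 points and significance, not for an interval width. A reader might infer that the trial's conclusion is in danger. At 4.4 true standard errors it probably is not. The interval is still the plan's statement of precision around a difference that will be read against 15 points.

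Fifth, median regression is only to be considered, and 7.2.1 does not say that it would replace the mean contrast. Mean and median differences diverge only if %EWL is skewed, which the documents do not quantify. This limits the point to a change of estimand that the wording permits.

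**Conclusion.** The concern holds as a gap in pre-specification with a foreseeable consequence, and it should be fixed. The plan expects unequal variances, assumes equal ones in its only primary test, and names no response that keeps the comparison of means.

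If a common variance is fitted at 80:120 with ESG SD 30, type I error for equal means is 10.6% with the planned LS SD of 5, and the interval is about 17.5% too narrow (1 − 0.825). Type I error falls to 7.5% at LS SD 17.8 and to 5.0% at LS SD 30. These figures are illustrative. They assume complete data and SDs constant over visits, and that covariate adjustment leaves the SD ratio unchanged. Neither power nor the likely direction of the result is in question.

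**What to change.** In 7.2.1, replace the sentences on covariance and on assumption checks with wording such as:

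> Residual variance will differ by arm and by visit, with a spatial correlation; if this does not converge, arm-specific variance with a spatial correlation and robust (sandwich) standard errors will be used. The primary contrast is the week-52 difference in mean %EWL from the treatment-by-visit terms, whatever the residual diagnostics show. Hierarchical median regression is a sensitivity analysis only.

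Robust standard errors on a constant-variance model should be a fallback, not an equal alternative. They leave the bias that can arise under the missing-at-random dropout assumed in 7.3 when variance grows over visits.

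The cost is wording only, with no change to sample size or data collection. The interval becomes wider: half-width 6.6 instead of 5.5 points with SDs 30 and 5, or 7.3 instead of 6.6 with LS SD 17.8. Covariance parameters rise from 2 for a common spatial structure to 4 with variance and correlation by arm, and to at most 24 with a variance for each arm at each of 11 visits (2 × 11 + 2). Power for 15 points stays at 94.5% or above in every case in step 5, and the analysis then matches the method used to size the trial.
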